### **10.5 Missed Doses**

If subjects miss a dose and recall the missed dose within 6 hours, they should take their dose with food. If more than 6 hours have elapsed after their usual dosing time, they should skip that dose and resume their normal schedule for the following dose.

### **10.6 Study Drug Interruption**

If LUM/IVA dosing must be interrupted due to AEs for more than 72 hours, the medical monitor must be notified. In these instances, LUM/IVA dosing may resume only after approval by the medical monitor. Specific instructions for interruption for elevated liver function test (LFT) levels are provided in Section 11.5.3.

### **10.7 Packaging and Labeling**

At the start of the study, Vertex or designee will provide a labeled supply of LUM/IVA combination therapy to the central pharmacy via the treating physician's request.

LUM/IVA tablets will be supplied in blister cards by Vertex. A detailed dispensation plan, including dispensation into Smart Pill Bottles, will be provided in the Reference Manual.

LUM/IVA labeling will be in compliance with applicable local and national regulations. Additional details regarding packaging, labeling, and dispensing for LUM/IVA will be included in the Pharmacy Manual.

### **10.8 Study Drug and Smart Adherence Technology Supply, Storage, and Handling**

LUM/IVA (200 mg/125 mg) will be supplied as pink film-coated tablets containing 200 mg LUM/125 mg IVA.

Blister cards must be stored under conditions noted in Table 10-2. While at the clinical site, the LUM/IVA must be stored in a secure and temperature-monitored area of limited access.

Instructions regarding the ordering, storage, and handling of LUM/IVA after dispensation to subjects will be provided to sites in the Reference Manual.

The investigator, or an authorized designee (e.g., a licensed pharmacist), will ensure that all LUM/IVA is stored in a secured area, under recommended storage conditions, and in accordance with applicable regulatory requirements. To ensure adequate records, all LUM/IVA will be accounted for via the drug accountability forms as instructed by Vertex.

**Table 10-2 Identity of LUM/IVA, Dosage, and Storage**

Drug Name	Strength/Formulation/Route	Dosage	Storage Condition
LUM/IVA (200 mg/125 mg)	200 mg/125 mg tablet; oral	LUM 400 mg / IVA 250 mg q12h	≤30°C (≤86°F)

IVA: ivacaftor; LUM: lumacaftor; q12h: every 12 hours

## **10.9 Drug and Smart Adherence Technology Accountability**

The pharmacist or designated study site staff will maintain information regarding the dates and amounts of (1) LUM/IVA received, (2) LUM/IVA dispensed to the subjects, (3) LUM/IVA returned by the subjects, (4) smart pill bottles received, (5) smart pill bottles dispensed to subjects, and (6) smart pill bottles returned by subjects. Subjects will be instructed to return all used and unused materials associated with LUM/IVA, including the assigned smart pill bottle, to the site. These materials will be retained at the site according to instructions provided by Vertex or its designee until inventoried by the study monitor. The study monitor will review LUM/IVA records and inventory throughout the study.

## **10.10 Disposal, Return, or Retention of Unused Drug**

The study site staff or pharmacy personnel will retain all materials returned by the subjects until the study monitor has performed drug accountability. At the end of the study, the study monitor will provide instructions as to the disposition of any unused LUM/IVA. If the study monitor authorizes destruction at the study site, the investigator will ensure that the materials are destroyed in compliance with applicable environmental regulations, institutional policy, and any special instructions provided by Vertex. Destruction will be adequately documented.

## **10.11 Blinding and Unblinding**

This will be a study of adherence with a deactivated smart adherence technology control arm. LUM/IVA treatment will be given open-label.

# **11 ASSESSMENTS**

## **11.1 Timing of Assessments**

The timing of assessments is shown in [Table 3-1](#) and [Table 3-2](#).

## **11.2 Subject and Disease Characteristics**

Subject and disease characteristics include the following: demographics, medical history, height, and weight. Based on the medical history, the subject will be assessed for any disqualifying medical conditions as specified in the inclusion and exclusion criteria. The medical history shall include a complete review of systems, past medical and surgical histories, and any allergies.

## **11.3 Adherence**

### **11.3.1 Smart Adherence Technology-Reported Adherence**

LUM/IVA adherence monitoring will occur throughout the Treatment Period using smart adherence technology. This technology will allow for collection of real-time LUM/IVA compliance by reporting LUM/IVA dosing times each time the smart pill bottles are opened. Only subjects in Study Arm A will review data with study physicians at the study visits listed in [Table 3-2](#).

## **11.5 Safety**

Safety evaluations will include AEs, clinical laboratory assessments, ophthalmologic examinations (for subjects <18 years of age), clinical evaluation of vital signs, and physical examinations (PEs).

### 11.5.1 Adverse Events

All AEs will be assessed, documented, and reported in accordance with ICH GCP guidelines. Section 13.1 outlines the definitions, collection periods, criteria, and procedures for documenting, grading, and reporting AEs. A separate document that details AE eCRF completion guidelines for investigators as well as training will be provided.

### 11.5.2 Clinical Laboratory Assessments

Blood samples and urine pregnancy tests will be analyzed at a central laboratory.

Blood and urine samples for clinical laboratory assessments will be collected as shown in [Table 3-1](#) and [Table 3-2](#). On Day 1, blood draws will be collected before the first dose of LUM/IVA. Laboratory test results that are abnormal and considered clinically significant will be reported as AEs (Section 13.1.1).

The safety laboratory test panels are shown in Table 11-1.

**Table 11-1 Safety Laboratory Test Panels**

Serum Chemistry	Hematology
Total Bilirubin, direct bilirubin	Hemoglobin
Alkaline phosphatase	Erythrocytes:
Aspartate aminotransferase	Mean corpuscular hemoglobin
Alanine aminotransferase	Mean corpuscular hemoglobin concentration
Gamma-glutamyl transferase	Mean corpuscular volume
	Platelets
	Reticulocytes (absolute)
	Leukocytes
	Differential (absolute and percent):
	Eosinophils
	Basophils
	Neutrophils
	Lymphocytes
	Monocytes

**Pregnancy ( $\beta$ -human chorionic gonadotropin) Tests for Females of Childbearing Potential:** Serum (Screening only) and urine pregnancy tests will be performed at the site as specified in [Table 3-1](#) and [Table 3-2](#). The serum and urine pregnancy tests will be analyzed at the central laboratory. The urine pregnancy test on Day 1 must be negative before the first dose of LUM/IVA. Additional urine pregnancy tests may be required according to local regulations and/or requirements

If a urine pregnancy test is positive, all LUM/IVA dosing will stop and the pregnancy will be confirmed with a serum  $\beta$ -human chorionic gonadotropin test. If confirmed, the pregnancy will be reported and the subject will be permanently withdrawn from LUM/IVA (Section 11.5.7.2). If a pregnancy test is positive, the procedures outlined in Section 11.5.7.2 will be followed.

**Follicle-stimulating hormone (FSH) (Screening Period only):** Blood sample for FSH will be measured for any suspected postmenopausal female with at least 12 months of continuous

spontaneous amenorrhea. Serum FSH levels must be within the postmenopausal reference range of the performing laboratory to be considered postmenopausal.

CFTR genotype (Screening Period only): *CFTR* genotyping will be performed to confirm the subject is homozygous for the *F508del-CFTR* mutation as documented in the subject's medical record. The results of the genotype must be obtained and reviewed during the Screening Period. CF genotyping can be waived if the subject has a documented genotype result from a previous Vertex study with a Screening Visit date of 01 June 2010 or later. Specific instructions will be provided in the Laboratory Manual.

Additional Evaluations: Additional clinical laboratory evaluations will be performed at other times if judged to be clinically appropriate.

For purposes of study conduct, only laboratory tests done in the central laboratory may be used. Local laboratories may be used at the discretion of the local investigator for management of urgent medical issues. If a local laboratory test value is found to be abnormal and clinically significant, it will be verified by the central laboratory as soon as possible after the investigator becomes aware of the abnormal result. If it is not possible to send a timely specimen to the central laboratory (e.g., the subject was hospitalized elsewhere), the investigator may base the assessment of an AE on the local laboratory value.

### **11.5.3 Liver Function Test Parameters**

#### Mandatory Liver Function Testing

Liver function testing (ALT, AST, GGT, ALP, and total bilirubin) must be performed as noted in [Table 3-1](#) and [Table 3-2](#).

It is strongly recommended that subjects with new treatment-emergent ALT or AST elevations of  $>3 \times$  ULN, total bilirubin  $>2 \times$  ULN, or clinical symptoms be followed closely, including repeat confirmatory testing performed by the central laboratory within 48 to 72 hours of the initial finding and subsequent close monitoring of ALT, AST and bilirubin levels, as clinically indicated. If ALT or AST is  $>5 \times$  ULN, follow-up levels must be obtained within  $7 \pm 2$  days.

If a subject cannot return to the site for liver function testing, a local laboratory may be used. Elevations in LFTs at the local laboratory must be reported immediately to the medical monitor, and the subject must have the tests repeated and sent to the central laboratory as soon as possible (ideally within 48 to 72 hours).

#### LUM/IVA Interruption

LUM/IVA administration must be interrupted immediately and the medical monitor must be notified if any of the following criteria is met:

- ALT or AST  $>5 \times$  ULN
- ALT or AST  $>3 \times$  ULN, in association with total bilirubin  $>2 \times$  ULN

A thorough investigation of potential causes should be conducted and the subject should be followed closely for clinical progression.

#### Resumption of LUM/IVA

LUM/IVA may be resumed when transaminases return to baseline or are  $\leq 2 \times$  ULN, whichever is higher. Approval by the medical monitor is required before resumption of LUM/IVA. Upon

resumption of LUM/, transaminases should be assessed weekly for 4 weeks. If a protocol-defined transaminase elevation occurs within 4 weeks of rechallenge with the LUM/IVA, then LUM/IVA must be interrupted again as outlined above.

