### **9.4 Removal of Subjects**

Subjects may withdraw from the study at any time at their own request and subjects may be withdrawn at any time at the discretion of the treating physician or by Vertex for safety, behavior, noncompliance with study procedures, or administrative reasons. LUM/IVA treatment will be withdrawn for any female subject who has confirmed pregnancy and for any male subject whose female partner has a confirmed pregnancy. A subject may be withdrawn from the LUM/IVA treatment after a discussion between the investigator and the medical monitor for any of the following reasons:

- A subject develops a medical condition that requires prolonged concomitant therapy with a prohibited medication or prolonged interruption of LUM/IVA combination therapy.
- A subject develops a life-threatening adverse event or a serious adverse event (SAE) that places him/her at immediate risk, and discontinuation of treatment with LUM/IVA and withdrawal from the study are deemed necessary
- A subject is noncompliant with the study requirements
- A subject has an increase in transaminases (ALT or AST), meeting criteria for interruption of LUM/IVA in Section 11.5.3.

A subject should be discontinued from the study for the following reason:

A subject on a transplant list undergoes lung transplantation

If a subject does not return for a scheduled visit, reasonable effort will be made to contact the subject. In any circumstance, reasonable effort will be made to document subject outcome. The investigator will inquire about the reason for withdrawal, request that the subject return all unused LUM/IVA, request that the subject return for a Safety Follow-up Visit, if applicable (see Section 8.1.4), and follow up with the subject regarding any unresolved AEs.

If the subject withdraws consent for the study, no further evaluations will be performed and no additional data will be collected. Vertex may retain and continue to use any data collected before such withdrawal of consent.

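### After a liver stop that depends on bilirubin, the written restart limit looks only at transaminases, so it can be met while bilirubin is still above 2×ULN

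*Protocol*

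**What the plan says.** Protocol Section 11.5.3 has three parts that matter here.

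- **Stopping.** Under *LUM/IVA Interruption*, dosing must stop at once if either of two criteria is met: ALT or AST above 5×ULN, or ALT or AST above 3×ULN "in association with total bilirubin" above 2×ULN. The same part adds: "A thorough investigation of potential causes should be conducted and the subject should be followed closely for clinical progression".
- **Restarting.** Under *Resumption of LUM/IVA*: "LUM/IVA may be resumed when transaminases return to baseline or are" no more than 2×ULN, whichever is higher. The medical monitor must approve.
- **After restart.** The same paragraph says "transaminases should be assessed weekly for 4 weeks", and then: "If a protocol-defined transaminase elevation occurs within 4 weeks of rechallenge with the LUM/IVA, then LUM/IVA must be interrupted again as outlined above".

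Under *Mandatory Liver Function Testing*, follow-up of new elevations is strongly recommended and includes "subsequent close monitoring of ALT, AST and bilirubin levels, as clinically indicated". This is not tied to restart.

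Other sections lead back to the same place. Section 10.6 says "Specific instructions for interruption for elevated liver function test (LFT) levels are provided in Section 11.5.3". Section 9.4 allows withdrawal for a transaminase increase "meeting criteria for interruption of LUM/IVA in Section 11.5.3". The SAP adds no restart rule. Nothing in Section 11.5.3 is redacted on this point.

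**The concern.** Bilirubin is half of one mandatory stopping criterion but is absent from the condition for ending that stop. Transaminases can recover, or in one situation never need to change, while the bilirubin finding that caused the stop persists. The written limit would then allow the medical monitor to approve restart without any stated requirement that bilirubin has come down.

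The same omission affects rechallenge. The weekly tests that must be done cannot show whether the combined criterion is met again. What is at stake is the safety of a very small number of subjects. The trial's comparison of adherence is not at stake.

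**Working it through.** The protocol states no figure to reproduce, so the check sets the rules side by side and runs cases through them.

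**Inputs**
- Stop (11.5.3): ALT/AST >5, or ALT/AST >3 with bilirubin >2 (all in ×ULN).
- Restart limit (11.5.3): ALT/AST ≤ max(baseline, 2).
- Entry (9.2, criterion 5): excluded if ALT/AST >5, or if ALT/AST >3 with bilirubin >2. A subject with ALT 4 and bilirubin 1 is therefore admitted, and so is one with ALT 2 and bilirubin 2.5.
- Baseline: Table 3-2 requires a pre-dose Day 1 liver panel that includes total bilirubin. The cases assume that the Day 1 values equal those at screening.

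**Cases** (ALT/bilirubin, ×ULN; the proposed text is the one under the fix)

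| Case | Baseline | At stop | At restart decision | Written limit | Proposed text |
|---|---|---|---|---|---|
| 1 | 1/1 | 4/2.5 | 2/2.5 | Met: 2 ≤ max(1, 2) = 2 | Not met: 2.5 > max(1, 2) = 2 |
| 2 | 4/1 | 4/2.5 | 4/2.5, same draw | Met: 4 ≤ max(4, 2) = 4 | Not met: 4 > 3 and 2.5 > 2, so the stop criterion is still present |
| 3 | 2/2.5 | 4/2.5 | 2/2.5 | Met: 2 ≤ max(2, 2) = 2 | Met: 2.5 ≤ max(2.5, 2) = 2.5, and ALT is not >3 |
| 4 | 1/1 | 6/1 | 2/2.5 | Met: 2 ≤ max(1, 2) = 2 | Met: bilirubin played no part in the stop, and ALT is not >3 |

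Case 2 is the clearest. The stop rule and the written restart limit are both satisfied by one set of results. Case 1 shows the gap for a subject with normal baseline values. Cases 3 and 4 check that the fix neither bars a subject admitted with raised bilirubin for good nor adds a bilirubin limit where bilirubin did not cause the stop.

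**Weekly tests after restart**
- ALT/AST >5: stop, whatever the bilirubin.
- ALT/AST ≤3: no stop, whatever the bilirubin.
- ALT/AST >3 to 5: stop only if bilirubin >2.

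Bilirubin decides only in the third band, and it is named in 0 of the 4 weekly tests.

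**Size** (rates are assumptions)
- Interrupted under the combined criterion, 0.5% to 2% of the planned 75: 75 × 0.005 = 0.375 to 75 × 0.02 = 1.5 subjects.
- Bilirubin still >2×ULN when ALT/AST meets the limit, 10% to 50% of those: 0.375 × 0.10 = 0.0375 to 1.5 × 0.50 = 0.75 subjects.

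**Effect on adherence.** SAP Section 8.3.2 removes days interrupted for reasons other than non-compliance from both numerator and denominator, so the effect on the endpoint is negligible.

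**The case against.** The strongest defence is that the wording fits the protocol's own logic. Both stopping criteria need a transaminase elevation. Bilirubin above 2×ULN alone neither excludes a subject nor stops dosing. The subject in case 1, with ALT 2 and bilirubin 2.5×ULN, could have enrolled or kept dosing with those values. This carries some weight for case 1, where asking for more is a clinical judgement. It does not answer case 2, where the stopping criterion is still met at the moment the restart limit is satisfied.

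The second defence is that restart is permitted, not automatic. The medical monitor has been told of the stop and must approve, causes must be investigated, and close monitoring that includes bilirubin is strongly recommended. All of this stands and lowers the risk. None of it states a bilirubin condition for restart.

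A reader might infer more than the documents support, in three ways.

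- *That a bilirubin rise after restart could go unseen until the next scheduled panel, with a stop missed.* While ALT/AST is at or below 3×ULN, no bilirubin value requires a stop. Once ALT/AST is newly above 3×ULN, the protocol strongly recommends confirmatory testing within 48 to 72 hours and monitoring that includes bilirubin. The full interval between scheduled visits applies only if restart falls at such a visit, and that visit's panel already contains bilirubin.
- *That the monitor has no bilirubin cutoff at all.* Section 11.5.3 gives 2×ULN in both the follow-up advice and the stopping rule. What is missing is its link to restart.
- *That every liver interruption needs a bilirubin limit for restart.* The criterion of ALT/AST above 5×ULN makes no use of bilirubin, so the defect shown does not extend to it.

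**Conclusion.** The point holds as a fault in a stated rule: the restart limit in Section 11.5.3 does not mirror the combined stopping criterion. It can be met with bilirubin still above 2×ULN, and for a subject enrolled with ALT above 3 and up to 5×ULN it can be met on the draw that caused the stop. The weekly tests share the omission, but there the gain from correcting it is narrower: the combined criterion could be judged at once when ALT/AST is above 3 and up to 5×ULN, without waiting for recommended follow-up.

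The size is small. Under the assumed rates, 0.04 to 0.75 subjects would be affected. That range uses the planned 75, and the documents do not give actual enrolment for a study that ended early, so it may overstate the number. This is a cheap safety improvement to consider. The textual finding is firm and rests on no assumed rate.

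**What to change.** In Section 11.5.3, replace the *Resumption of LUM/IVA* paragraph with text to this effect:

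> With medical-monitor approval, LUM/IVA may restart only if (a) ALT and AST are each no higher than the larger of the subject's baseline and 2×ULN; (b) neither interruption criterion is currently met; and (c) where the combined criterion was met at the interruption, alone or together with the other, total bilirubin is also no higher than the larger of baseline and 2×ULN. After restart, ALT, AST and total bilirubin are measured weekly for 4 weeks, and dosing is interrupted again if either criterion is met.

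The 2×ULN value is the cutoff the protocol already uses for bilirubin in Sections 9.2 and 11.5.3. The sponsor may prefer a lower one.

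**Cost.** One paragraph changes, and one analyte already in the central panel (Table 11-1) is added to at most four draws per resumed subject. If 1% to 5% of 75 subjects resume after a liver interruption (an assumption), that is 75 × 0.01 × 4 = 3 to 75 × 0.05 × 4 = 15 extra bilirubin results in the whole trial. The downside is a possibly later restart for very few subjects. Since SAP Section 3 records early termination, the change helps only subjects still dosing or a later protocol that reuses this section.

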#### **11.5.4 Physical Examinations and Vital Signs**

Complete and symptom-directed physical examinations (PE) of body systems and vital signs assessment will be performed as listed in [Table 3-1](#) and [Table 3-2](#). Additional symptom-directed PEs and symptom-directed vital sign assessments can be performed at the discretion of the investigator or healthcare provider.

A complete PE includes a review of the following systems: head/neck/thyroid; eyes/ears/nose/throat (EENT); respiratory; cardiovascular; lymph nodes; abdomen; skin; musculoskeletal; and neurological. Breast, anorectal, and genital examinations will be performed when medically indicated. After screening, any clinically significant abnormal findings in PEs will be reported as AEs.

The abbreviated PE will include an assessment of the following body systems: EENT, cardiovascular system, respiratory system, abdomen, and skin

Vital signs include blood pressure (systolic and diastolic), oral temperature, pulse rate (beats per minute [bpm]), and respiration rate (breaths per minute). These will be assessed following a 5-minute rest in the seated or supine position.

#### **11.5.5 Spirometry**

Spirometry will be performed according to the American Thoracic Society Guidelines as noted in [Table 3-1](#) according to the additional guidelines that follow.

During the Screening Visit, a spirometry assessment may be performed pre- or postbronchodilator. The spirometry assessment will be recorded in the source documents as prebronchodilator or postbronchodilator.

The parameters listed below will be normalized using the standards of Wang et al., (for male subjects aged 12 through 17 years) or Hankinson et al., (for female subjects aged 16 years and older and male subjects aged 18 years and older).

- FEV1 (L)
- Forced vital capacity (FVC) (L)
- FEV1/FVC (ratio)
- Forced expiratory flow (FEF25%-75%) (L/s)

#### **11.5.6 Ophthalmologic Examination**

Subjects who are <18 years old at Day 1 will undergo an ophthalmologic examination at the Screening and Week 48 visits. The exam will be performed by either a licensed ophthalmologist or optometrist, as noted in [Table 3-1](#) and [Table 3-2](#), and will include:

- measurement of best corrected distance visual acuity of each eye;
- pharmacologically dilated examination of the lens with a slit lamp.

The screening ophthalmologic examination must be completed and the results reviewed before enrollment. This examination does not have to be repeated if there is documentation of an examination that met protocol criteria within 3 months before the date of informed consent (or assent, when applicable) or if there is documentation of bilateral lens removal for the subject.

If a cataract or lens opacity is identified and determined to be clinically significant by the ophthalmologist or optometrist at the Screening examination, the subject (and the subject's parent or guardian if the subject is a minor) will be notified. Additional ophthalmologic examinations may be conducted at the discretion of the investigator. The Vertex medical monitor or designee should be notified of any additional ophthalmologic examinations.

If a cataract or lens opacity is identified and determined to be clinically significant by the ophthalmologist or optometrist after dosing, the subject will be notified. After discussion with the Principal Investigator and in collaboration with the medical monitor, the subject may elect to continue or discontinue LUM/IVA treatment. If the subject discontinues LUM/IVA treatment, the subject should complete the Safety Follow-up Visit. If the subject continues IVA treatment, more frequent ophthalmologic monitoring should be considered.

In addition, at screening, the following history will be obtained and documented for all subjects:

- History of steroid use
- History or presence of diabetes
- Any prior ophthalmologic examinations
- History of trauma to the eye
- Any family history of glaucoma, congenital cataracts, or cataracts arising later in life
- Use of corrective lenses (contact lenses or eyeglasses)
- History of prolonged exposure to sunlight or ultraviolet light and use of sunglasses
- History of exposure to secondhand smoke

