**Table 3-2 Treatment Period and Safety Follow-up Visit Assessments – Study VX15-809-114**

Event/Assessment	Day 1	Week 12	Week 24	Week 36	Week 48	Safety Follow-up Week 52 a
Clinic visit	X	X	X	X	X	X
Vital signs b	X	X	X	X	X	X
Physical examination c					X	X d
Liver Function Testing e	X	X	X	X	X	X
Urine pregnancy test (all female subjects of childbearing potential)	X	X	X	X	X	X
Randomization f	X					
Standardized education on adherence	X					
Concomitant medications, treatments, and procedures	X	X	X	X	X	X
Smart Adherence Technology-Reported Adherence g		X	X	X	X	

LUM/IVA drug count i		X	X	X	X	
Ophthalmologic examination j					X	
AEs and SAEs	Continuous from signing of ICF or assent (where applicable)					
LUM/IVA resupply	Every 3 months throughout study					

AE: adverse event; ICF: informed consent form; IVA: ivacaftor; IWRS: interactive web response system; LUM: lumacaftor; PE: physical examination; SAE: serious adverse event; [REDACTED]

a The Safety Follow-up Visit is 28 ( $\pm$  7) days after the last dose of LUM/IVA (Section 8.1.3).

b Vital signs will be assessed following a 5-minute rest in the seated or supine position.

c Symptom-targeted PEs will occur at any time during the study if triggered by AEs or if deemed necessary by the investigator.

d Required for subjects who do not begin commercial LUM/IVA after Week 48 only.

e Day 1 only blood draws will be collected before the first dose of LUM/IVA. Liver function testing (alanine aminotransferase [ALT], aspartate aminotransferase [AST], gamma-glutamyl transpeptidase [GGT], alkaline phosphatase [ALP], and total bilirubin) must be performed at the scheduled visits (Section 11.5.2).

f Randomization must occur after all inclusion and exclusion criteria are met and before the first dose of LUM/IVA. Randomization will be done through IWRS.

g Data will be collected for all subjects throughout the study in real-time. Subjects in Study Arm A will review data with physicians at study visits.

i LUM/IVA drug count will be collected at the end of specified study visits.

j See Section 11.5.6.

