### 8.1.4 Early Termination of Treatment

Subjects who prematurely discontinue LUM/IVA treatment for any reason (except withdrawal of consent or assent) and who do not begin commercial LUM/IVA will be asked to return to the clinical site 28 ( $\pm$  7) days of their last dose of LUM/IVA for a Safety Follow-up Visit.

Assessments performed at this visit will be the same for those in the Safety Follow-up Visit ([Table 3-2](#)).

If the subject withdraws consent or assent for the study, no further evaluations should be performed and no additional data should be collected. Vertex may retain and continue to use any data collected before such withdrawal of consent.

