### Ophthalmologic Examinations

Cases of noncongenital lens opacities have occurred in pediatric patients treated with ivacaftor, a component of LUM/IVA. Although other risk factors were present in some cases (such as corticosteroid use and exposure to radiation), a possible risk attributable to ivacaftor cannot be excluded. Baseline and follow-up ophthalmological examinations are recommended in pediatric patients initiating LUM/IVA treatment (See Section [11.5.6](#))

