### **12.3.5 Safety Analysis**

All safety analyses will be based on the set of data associated with the treatment-emergent period for subjects in the Safety Set.

The overall safety profile of LUM/IVA will be assessed based on the following safety and tolerability endpoints:

- Treatment-emergent adverse events (TEAEs)
- Clinical laboratory values (i.e., liver function tests)
- Vital signs
- Ophthalmological examinations

All safety data will be presented in individual subject data listings.

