3 INTRODUCTION

This statistical analysis plan (SAP) Methods describes the final analysis for Study VX15-809-114 and is based on the following:

- approved clinical study protocol (Version 2.0, dated 19 October 2016)
- approved electronic case report form (eCRF) (Version 2.0, dated 22 December 2016)

Study VX15-809-114 is a Phase 4, open-label treatment, randomized, multicenter, 2-arm, parallel-group, pilot study of adherence to lumacaftor/ivacaftor (LUM/IVA) in cystic fibrosis (CF) subjects homozygous for *F508del*.

This study was terminated early by a business decision. The collected data at the time of termination are limited and therefore, the planned statistical analyses in the protocol will not be performed. Descriptive summary of statistics will be performed. Please refer to Section 8 for details.

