8.4.4 Ophthalmological Examinations

Listings for subjects with abnormal ophthalmological examinations for subjects <18 years old at screening will be provided.

Listings for ophthalmological history data for all subjects will be provided.

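### For subjects under 18 the only scheduled follow-up eye examination is at Week 48 and none is required after an earlier stop, so the SAP's abnormal-only listing cannot tell a normal follow-up from no follow-up

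*Protocol*

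**What the plan says.** Protocol Section 8.2.3 notes lens opacities in pediatric patients treated with ivacaftor, says a drug contribution cannot be ruled out, and adds: "Baseline and follow-up ophthalmological examinations are recommended in pediatric patients initiating LUM/IVA treatment".

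Section 11.5.6 sets the schedule: "Subjects who are <18 years old at Day 1 will undergo an ophthalmologic examination at the Screening and Week 48 visits". Table 3-2 and its copy in SAP Table 11-2 agree. The row has one mark, at Week 48, and the Safety Follow-up column is blank. Section 11.5.6 also lets the investigator order further examinations.

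For early stoppers, Section 8.1.4 provides a visit 28 (± 7) days after the last dose: "Assessments performed at this visit will be the same for those in the Safety Follow-up Visit". Sections 8.1.3 and 8.1.4 excuse subjects who start commercial LUM/IVA.

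Protocol Section 12.3.5 and SAP Section 8.4 both name eye examinations among four safety endpoints. The protocol says: "All safety data will be presented in individual subject data listings". SAP Section 8.4.4 says: "Listings for subjects with abnormal ophthalmological examinations for subjects <18 years old at screening will be provided". It adds a listing of eye history for all subjects. SAP Section 3 records: "This study was terminated early by a business decision".

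**The concern.** The protocol singles out one risk for its youngest subjects and pairs a baseline with a follow-up examination to watch for it. The follow-up half depends on reaching Week 48. A study stopped early is the setting in which many subjects may not get there.

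Reporting adds to the problem. A listing restricted to abnormal results has no denominator. If it is empty, the reader cannot tell whether minors were re-examined and were normal, or were not re-examined at all. At stake is whether the study report can say anything about lens findings in minors, and whether it shows how little it can say.

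**Working it through.** The plan states no figure on this point, so there is nothing to reproduce. The check sets the sections side by side and then gives one illustration on assumed counts.

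**Step 1: what is required of a subject under 18 at Day 1.**

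| Path | Visit required | Follow-up eye examination required |
|---|---|---|
| Reaches Week 48 | Week 48 | Yes (Section 11.5.6, Table 3-2) |
| Stops earlier, no commercial LUM/IVA | Safety Follow-up | No (Section 8.1.4, Table 3-2) |
| Stops earlier, starts commercial LUM/IVA | None | No (Sections 8.1.3 and 8.1.4) |

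Section 8.1 says that all subjects complete the assessments of all scheduled visits, which could be read as keeping early stoppers to Week 48. The sentence after it sends them to the Safety Follow-up Visit, and Section 8.1.4 confirms that route. Table 3-2 does carry the Week 48 physical examination into the Safety Follow-up column, with a condition (footnote d). It has no matching entry for the eye examination.

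**Step 2: what the outputs show for the four safety endpoints.**

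| Endpoint | SAP output | Are normal results or numbers assessed visible? |
|---|---|---|
| Treatment-emergent adverse events | Tables by arm (8.4.1) | Yes |
| Liver function tests | Values and changes summarized by visit (8.4.2) | Yes |
| Vital signs | Results listed (8.4.3) | Yes |
| Eye examinations | Abnormal examinations listed (8.4.4) | No |

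The eye-history listing covers information that Section 11.5.6 collects at screening. The discontinuation listing (SAP 8.2.1) shows who stopped, and the exposure categories (SAP 8.2.5) show for how long, by group. Neither shows who was examined. The protocol has no separate subsection on analysing eye examinations, so its general promise of listings is the only output it specifies for them, and SAP 8.4.4 is narrower.

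**Step 3: the age rule.** Section 11.5.6 uses age at Day 1 and SAP 8.4.4 uses age at screening. A subject who turns 18 between the two is in the SAP group but is not required to have the Week 48 examination.

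**Step 4: illustration.** The number of minors is not given, so 5, 10 and 15 are assumptions. With no abnormal findings among k subjects examined after baseline, the exact one-sided 95% upper bound p on the finding rate solves (1 − p)^k = 0.05, so p = 1 − 0.05^(1/k). For k = 10, 0.05^(1/10) = 0.741 and p = 25.9%.

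| Minors (assumed) | Examined after baseline (k) | Upper bound |
|---|---|---|
| 5 | 5 | 45.1% |
| 5 | 1 | 95.0% |
| 10 | 10 | 25.9% |
| 10 | 5 | 45.1% |
| 10 | 2 | 77.6% |
| 15 | 15 | 18.1% |
| 15 | 8 | 31.2% |
| 15 | 3 | 63.2% |
| any | 0 | 100% (no information) |

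The planned listing is empty in every row.

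**The case against.** The strongest reply is that the schedule is coherent. Section 8.2.3 sets no time for the follow-up examination and does not mention early stoppers. Section 11.5.6 and both schedule tables provide one examination of each kind. This largely stands: the schedule is a design choice that leaves a gap. The only real ambiguity is the Section 8.1 sentence noted in Step 1.

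Second, extra examinations are allowed. That stands too. A reader might infer that early stoppers get no eye examination, but the documents support only that none is required.

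Third, other data bear on the eye. Adverse events are asked about at each visit, and a complete physical examination includes the eyes. This is fair as far as it goes, but neither replaces the dilated slit-lamp examination the protocol specifies.

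Fourth, abnormal-only listings are common in this SAP, including for hematology and physical examination, and the SAP says openly that its analyses were cut back after termination. However, physical examination and hematology are not among the four named endpoints, and liver tests also have a summary by visit.

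Fifth, a reader might take the Section 11.5.6 instruction "If the subject discontinues LUM/IVA treatment, the subject should complete the Safety Follow-up Visit" to mean that a subject who stops because of a lens opacity is lost to view. That does not follow. Such a subject has already had a post-baseline examination and would appear in the abnormal listing.

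Finally, the termination was a later business decision and does not show that the original design was faulty. A protocol change also comes too late to produce examinations in a terminated study. Both points stand, and they are why the SAP change comes first.

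**Conclusion.** The point holds as a reporting gap resting on a scheduling gap. No follow-up eye examination is required of a subject under 18 who stops before Week 48, and the planned output cannot separate a normal follow-up from none.

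Its size is unknown. Entry is at 16 years or older, so only 16- and 17-year-olds are concerned, and the documents give neither their number nor how many reached Week 48. The share without a required examination could be anywhere from 0 to 100%. A reader might infer from the termination, and from the replacement of the 48-week endpoints by any-duration and 12-week ones, that the share is large. The documents make missed examinations foreseeable but do not establish how many there were. Nor do they show that any lens finding was missed.

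The percentages in Step 4 rest on assumed counts and show only how much the missing denominator matters. The conclusion itself needs no assumption beyond the text.

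**What to change.** **Main change, SAP Section 8.4.4.** List every ophthalmologic examination for subjects under 18, with result (normal or abnormal) and study day, and show where none was done. Report by arm how many such subjects had a baseline examination and how many had a post-baseline one. Say how documented earlier examinations and bilateral lens removal, which Section 11.5.6 accepts in place of the screening examination, enter these counts. Use one age rule, Day 1 or screening, in both documents. The cost is one wider listing and one count, assuming the case report form records normal results and dates.

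**Secondary change, protocol.** Reconcile Sections 8.1, 8.1.4, 8.2.3 and 11.5.6 with Table 3-2, so that the text says what follow-up eye examination, if any, applies to a subject under 18 who stops before Week 48. Whether and when to examine is the sponsor's clinical decision. For this study the gain is mainly clarity, since it has already ended.
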